APPENDIX B: EMA QUESTIONS

Q1. Since the past alarm, how much have you had thoughts that you really can't trust other people?

(1 = not at all, 7 = very much)

Q2. Since the past alarm, how much have you been bothered by voices?

(1 = not at all, 7 = very much)

Q3. Since the past alarm, who have you interacted with? Select all that apply.

[haven't interacted with others; friends; spouse, partner, or other family; with roommates, co-workers, or others you know; with strangers; other people (please specify)]

Q4. How much interest or motivation did you have interacting with others since the last alarm?

(1 = not at all, 7 = very much)

Q5. How much pleasure or enjoyment did you feel in these interactions?

(1 = not at all, 7 = very much)

Q6. How did you feel toward others in the interactions?

(1 = on guard or threatened; 7 = trusting or warm)

Q7. What do you think others were thinking about you?

(1 = unlikeable or inferior; 7 = likeable or capable)

Q8. Since the past alarm, how much have you felt sad or depressed?

(1 = not at all, 7 = extremely)

Q9. Since the past alarm, how much have you felt energized or excited?

(1 = not at all, 7 = extremely)

Q10. Since the past alarm, how much have you been feeling like you belong or fit with others in your life?

(1 = not at all, 7 = extremely)

Q11. Since the past alarm, how much have you felt irritated or upset?

(1 = not at all, 7 = extremely)

Q12. Since the past alarm, how much have you felt that you were a burden on others?

(1 = not at all, 7 = extremely)

Q13. Since the past alarm, how much have you felt happy?

(1 = not at all, 7 = extremely)

Q14. How much interest or motivation do you have in interacting with others later today?

(1 = not at all, 7 = very much)

Q15. How much do you want to avoid others later today?

(1 = not at all, 7 = very much)

830 **References**

831 Adams, R. B., Gordon, H. L., Baird, A. A., Ambady, N., & Kleck, R. E. (2003). Effects of gaze
832 on amygdala sensitivity to anger and fear faces. *Science*, 300(5625), 1536–1536.
833 <https://doi.org/10.1126/science.1082244>

834

836 *Nature*, 393(6684), 470–474. <https://doi.org/10.1038/30982>

837

839 *Journal of Neuroscience*, 15(9), 5879–5891. <https://doi.org/10.1523/jneurosci.15-09-05879.1995>

841

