398 study, we intentionally overrecruited. Recruitment continued until the end of January 2024,
399 aligning with the anticipated completion of our data collection period. As a result, a total of 63
400 participants consented, 50 of whom were randomized and completed the study.

401 *4.2 Recruitment and Eligibility*

[figure not shown]
402 The current sample was recruited from a database of previous participants in our lab and
403 via mental health agencies in the Dallas-Fort Worth region. Study fliers were placed in outpatient
404 clinics, and interested individuals either contacted study personnel directly or asked to be
405 contacted by the study team. This recruitment approach has been consistently used by our
406 research team supervised by [name], and has been found to yield a substantial number
407 of participants, respect patient privacy, and minimize the possibility of coercion.

408 Eligible participants were between the ages of 18 and 64 inclusively, had a diagnosis of
409 schizophrenia or schizoaffective disorder, and demonstrated either current (in the past week) or
410 recent (in the past month) paranoia. Participants were not asked to change any part of their
411 current treatment regimen, and all medications were accepted. Participants were required to have
412 been clinically stable for a minimum of 6 weeks with no dose changes $>20\%$ for a minimum of
413 two weeks. Exclusion criteria included: 1) presence or history of a pervasive developmental
414 disorder or mental retardation as defined by $IQ < 70$, 2) presence or history of neurological or
415 medical disorders that contraindicate neural stimulation (e.g. presence or history of epilepsy,
416 seizures, etc.), 3) demonstrating sensory limitations, including uncorrectable visual or hearing
417 impairments that interfere with assessment, 4) history of electroconvulsive therapy, 5) lack of
418 proficiency in English, and 6) substance use disorder not in remission in the past 6 months.

419
420 **5. Procedure**

421 As shown in **Figure 1** below, this was a double-blind, within-subjects, crossover design
422 comparing the effects of active vs. sham tDCS. Participants completed 3 long visits (i.e., 1
423 enrollment visit, 2 stimulation visits). The 2 stimulation visits were at least a week apart (with an
424 average of 14.58 days between the stimulation visits in the current study) to make sure that the

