425 tDCS effects from the first visit dissipated, and the first simulation visit was expected to occur 7
426 days after the enrollment visit (average days = 13.59 days in the current study).

Day 1 —→ Day 2-8 —→ Day 9 —→ Day 10-16 —→ Day 17 —→ Day 18-24

427

[figure not shown]
428 **Figure 1. Flowchart of the study procedure**

429

430 **6. Stimulation Protocol**

431 *6.1 Stimulation Procedure*

432 After completing pre-stimulation assessments, participants started the first stimulation
433 procedure of the visit via neuroConn's programmable Direct Current stimulator. Electrodes were
434 affixed to the participant's head to target the stimulation area as determined for each individual
435 via the international 10-20 EEG placement system with Modified Combinatorial Nomenclature.
436 For stimulating the right VLPFC, the anode was placed over F6 (Montreal Neurological Institute
437 coordinates: 44, 32, -12 (Pinkham, Hopfinger, Ruparel, et al., 2008), and the contralateral
438 homolog area (F5) was targeted for the stimulation of the left VLPFC (see **Figure 2** for 10-20
439 EEG placement). Electrodes were placed identically for the control condition. Following the
440 neurostimulation procedure, participants were asked to remain seated in the chair and browse
441 through magazines quietly for 30 minutes to allow stimulation effects to stabilize (Samani et al.,
442 2019).

443

444 **Figure 2. 10-20 EEG placement**

[figure not shown]
445 6.2 Counterbalance and Randomization

446 The active stimulation and sham control conditions were counterbalanced, meaning that
447 each participant had the same possibility of experiencing either the active or sham condition at
448 the first visit, and the other condition at the second visit. In the current study, 26 participants
449 received the active stimulation at their Visit 1, while the remaining 24 received it at their Visit 2.
450 This counterbalance procedure was achieved via the “study mode” preprogrammed feature of the
451 NeuroConn machine, which randomly assigned participants to either the active stimulation or
452 sham group in a double-blinded way. Specifically, each participant received a 5-digit code,
453 which was paired with one active stimulation code and one sham control code to ensure that each
454 participant did not receive two stimulation or control conditions. After study completion, each
455 participant’s study code for that given visit was revealed and recorded. The project manager

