486 study. It reveals that our targeted VLPFC is one of the regions receiving the most intense
487 stimulation, along with the dorsal medial PFC and a portion of the DLPFC.

488

489 7. Assessments

490 7.1 Enrollment Visit

491 At the enrollment visit, consent was obtained from participants, and demographic
492 information was also collected. Paranoia screening and diagnostic interviews were performed to
493 determine eligibility. Current medications were reported by the patients, and they were asked to

494 remain on a stable dose of medication throughout their participation in the study unless
495 specifically recommended by their physician. After that, participants completed daily EMA
496 surveys for 7 days to assess baseline paranoia level and social functioning in daily life. They then
497 attended the first stimulation visit. At both stimulation visits, the Positive and Negative
498 Syndrome Scale (PANSS) (Kay et al., 1987) was administered by trained research personnel to
499 assess the full range of symptoms in individuals with SSD. Daily EMA surveys between
500 Stimulation Visit 1 and 2, as well as after Stimulation Visit 2, were also sent to participants to
501 monitor any changes in paranoia and social functioning after tDCS in the participant's day-to-
502 day life.

503 *7.2 Stimulation Visits: Pre-stimulation Assessments*

504 **Trait Paranoia.** The Paranoia Scale (PS) (Fenigstein & Venable, 1992) is a self-report
505 measure to assess trait paranoia. This measure contains 20 items (e.g., "Someone has it in for
506 me", "It is safer to trust no one") and is measured on a five-point Likert scale (1 = not at all
507 applicable, 5 = extremely applicable). Scores range from 20-100, with higher scores indicating
508 higher paranoia. The PS demonstrated good reliability and validity in previous work on patients
509 with schizophrenia (Pinkham et al., 2012; Tiernan et al., 2014). In the current study, PS showed
510 excellent internal consistency in both Stimulation Visit 1 (Cronbach's $\alpha = 0.941$) and Stimulation
511 Visit 2 (Cronbach's $\alpha = 0.930$).

512 **State Paranoia.** The State Social Paranoia Scale (SSPS) (Freeman et al., 2007) was used
513 to examine paranoia levels immediately before and at the conclusion of stimulation within each
514 visit. Participants indicated how much they agreed with each of 20 statements (e.g., "Someone
515 was hostile towards me", "Someone was trying to isolate me") using a five-point Likert scale (1

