590 multiplied by 100 to generate a percentage bias score, with a greater percentage indicating a
591 higher level of paranoid interpretation bias. Previous research has demonstrated moderate-to-
592 strong correlations between SST scores and paranoia (r fluctuates at around 0.4-0.6) (Savulich et
593 al., 2015, 2017).

594 **Hostility Scale of the Personality Inventory for DSM-5 (PID-5-HS):** PID-5-HS
595 (Krueger et al., 2012) contains 10 self-report items (e.g., "I snap at people when they do little
596 things that irritate me") assessing pathological hostility on a 4-point scale (0 = very false or often
597 false, 3 = very true or often true), with higher total scores indicating more hostility (range = 0-
598 30). PID-5-HS showed a high correlation with AIHQ blame score ($r = 0.47$) in previous research
599 (Buck et al., 2016). In the current study, the internal consistency of PID-5-HS was excellent
600 (Cronbach's $\alpha_{\text{visit 1}} = 0.902$, Cronbach's $\alpha_{\text{visit 2}} = 0.913$).

601 **Trustworthiness Task.** The trustworthiness task requires participants to indicate how
602 much they trust each of 60 grayscale facial stimuli along a 7-point Likert scale (-3 = very
603 untrustworthy, 3 = very trustworthy) (Adolphs et al., 1998). Total scores were calculated by
604 averaging across responses and hence varied from -3 to +3, with higher values indicating a
605 greater tendency to trust others. There is a small-to-medium association between trustworthiness
606 scores and paranoid ideation (r fluctuates between -0.1 and -0.3) (Buck et al., 2016; Klein et al.,
607 2018).

608

609 **8. Ecological Momentary Assessments**

610 EMA surveys were administered for a total of 21 days – 7 days prior to simulation visit 1,
611 7 days after stimulation visit 1, and 7 days after stimulation visit 2. Participants received 3
612 randomly timed surveys assessing current paranoid symptoms and social interactions each day.
613 The surveys were sent in the morning, mid-day, and evening, with random initiation at time
614 intervals ≥ 2 hours. Participants were allowed to respond to the survey within 1 hour after the
615 survey was sent. This protocol is in line with previous work and was demonstrated to yield ideal
616 intra-day variation and compliance (Jones, Moore, Depp, et al., 2021; Jones, Moore, Pinkham, et
617 al., 2021). Each survey queried the frequency of auditory hallucinations and paranoid ideation

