647 used to test the differences in daily feelings of paranoia (i.e., Q1) across the three EMA periods
648 (EMA-baseline vs. EMA-active vs. EMA-sham), with the condition of the EMA period being
649 dummy-coded.

650 **Hypothesis 2a:** To test the improvement in social functioning measured in the lab (active vs.
651 sham stimulation), paired-samples t-tests were performed for self-reported social functioning
652 measured only after the stimulation.

653 **Hypothesis 2b:** MLM with maximum likelihood robust estimation was used to test the
654 differences in daily social functioning (i.e., Q3, Q4, Q5, Q6, Q7, Q14, Q15) across the three
655 EMA periods (EMA-baseline vs. EMA-active vs. EMA-sham), with the condition of the EMA
656 period being dummy-coded.

657 Notably, one of the daily social functioning questions (i.e., Q3: Since the past alarm, who
658 have you interacted with?) has a different score range. It is quantified as the frequency of social
659 interactions, where a higher score indicates more interactions across a broader range of people
660 categories (range = 0-5). In contrast, the remaining six items adhere to a score range of 1-7.
661 Therefore, we performed MLM separately for Q3 (named as social interaction frequency) and for
662 the average of items Q4, Q5, Q6, Q7, Q14, and Q15 (named as social interaction motivation and
663 experience) for parsimony.

664

665 **10. Participant Payment**

666 Participants were compensated \$20 for completing the enrollment visit, \$100 for each of
667 the two in-lab stimulation visits, and up to \$16 for each of the 7-day EMA periods (three EMA
668 periods in total), totaling a maximum of \$268. Participants who enrolled in the study but were
669 found ineligible during screening were still compensated \$20. If participants stopped taking part
670 in the study or were withdrawn by the research team, they received \$5 for each 20 minutes
671 completed during the lab visits. For example, if they completed 1 hour of the study, they were
672 paid \$15. Compensation for each EMA period was determined by the number of surveys
673 completed, with \$0.75 paid for each survey except for the final survey, which was worth \$1 (to
674 allow for an even amount of \$16 per EMA period if all 21 surveys were completed). Parking on
675 campus was provided for participants.
676

677 **11. Risk and Benefits Assessments**

678 *11.1 Potential Risks*

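### The first EMA survey after each stimulation visit asks about time before that stimulation but is coded wholly to it; the dilution is small (about 4–5%) and a data-handling rule would remove it

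*Combined protocol and SAP*

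**What the plan says.** Appendix B gives the item wording. The paranoia item (Q1, the sole outcome for Hypothesis 1b) reads "Since the past alarm, how much have you had thoughts that you really can't trust other people". Q3, a separate outcome for Hypothesis 2b, reads "Since the past alarm, who have you interacted with? Select all that apply". Q4 reads "How much interest or motivation did you have interacting with others since the last alarm", and Q5–Q7 concern those same interactions. Q14 and Q15 ask only about the rest of the current day.

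Section 9 compares three periods, "EMA-baseline vs. EMA-active vs. EMA-sham), with the condition of the EMA period being" dummy-coded. Condition thus belongs to the period, not to the time that the answer describes.

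Section 8 places the two later EMA periods "7 days after stimulation visit 1, and 7 days after stimulation visit 2". The day line of Figure 1 has visits on Days 1, 9 and 17 and EMA on Days 2–8, 10–16 and 18–24, so each period starts the day after a visit. Section 5 reports mean intervals of 13.59 days from enrollment to Visit 1 and 14.58 days from Visit 1 to Visit 2.

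On the timing of baseline EMA, section 7.1 says that after the enrollment visit participants completed "surveys for 7 days to assess baseline paranoia level and social functioning in daily life. They then" went to the first stimulation visit. Section 8 describes the same period as the seven days before Visit 1.

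No section drops, rewords or flags the first survey of a period.

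**The concern.** Within a period the look-back is a matter of hours. Across the break between two periods it stretches to the last alarm of the preceding period, and the actual visit intervals were much longer than the eight days on the Figure 1 line. The first survey after a stimulation visit therefore mostly describes time before that stimulation, yet it enters the model as an outcome of it.

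Three things are at stake. Time before the stimulation is averaged into the active or sham outcome, which pulls the contrast toward zero. The affected survey is one of only three on the first day after stimulation, and section 11.2 describes tDCS effects as often temporary, so an early effect would be hit hardest. For Q3, which counts kinds of people met, a window of days can only hold or raise the count relative to a window of hours.

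**Working it through.** **Surveys per period.** Section 8 gives 3 surveys a day for 7 days: 3 × 7 = 21. Section 10 agrees: 20 × $0.75 + $1 = $16.

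**Look-back window.** Time without alarms before the stimulation = mean visit interval − 7 EMA days. Window of the first survey = that time + 1 day, taking the first survey to be sent the day after the visit, as on the Figure 1 day line.

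| Case | Before stimulation | Window | Share before |
|---|---|---|---|
| Third period (after Visit 2) | 14.58 − 7 = 7.58 d | 8.58 d | 7.58/8.58 = 88% |
| Second period, baseline EMA straight after enrollment (7.1) | 13.59 − 7 = 6.59 d | 7.59 d | 6.59/7.59 = 87% |
| Second period, baseline EMA in the week just before Visit 1 (one reading of section 8) | about 1 d | about 2 d | about 50% |
| Figure 1 schedule, either period | 1 d | 2 d | 50% |

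The third-period figure does not depend on when baseline EMA ran. The second-period figure does. In every case the first survey reaches back before the stimulation.

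**Share of surveys.** One of 21 scheduled surveys is 1/21 = 4.8%. Among participants who answered it, the share of answered surveys is 1/(21 × 0.8338) = 5.7% in the second period and 1/(21 × 0.8004) = 5.9% in the third, using the compliance figures in section 8. If the first survey is missed, the next one looks back only to the missed alarm. The expected share therefore remains about 4.8%.

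**Dilution.** Assume that the effect is constant over the period, that answers weight the window evenly, and that time before the stimulation carries no effect. The lost fraction is then the share of surveys times the share of the window before stimulation:

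- scheduled surveys: 0.88/21 = 4.2%;
- answered surveys, third period: 0.88 × 5.9% = 5.2%;
- answered surveys, second period under section 7.1: 0.87 × 5.7% = 5.0%;
- second period under the other reading of section 8, scheduled surveys: 0.5/21 = 2.4%.

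As an illustration only, the in-lab pilot effect of d = 0.51 (section 4.1) would become 0.51 × (1 − 0.042) = 0.49.

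**Q3.** The documents do not say how many contact categories a week-long window yields. Assuming 3 to 4 instead of 1, and about 17 answered surveys, the period mean rises by (3 − 1)/17 = 0.12 to (4 − 1)/17 = 0.18 on the 0–5 scale. The rise arises in both post-stimulation periods, hence once under active and once under sham.

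**The case against.** The strongest reply is that the effect is slight: one survey in 21, a loss of about 4–5% of a constant effect, and Q14 and Q15 untouched. That stands, and it sets the weight of the point.

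A reader might infer that the longer Q3 window biases active against sham. The documents do not support this. Each participant has one such survey under each condition, and order was nearly balanced (26 and 24, section 6.2), so the rise largely cancels. It matters mainly against baseline, whose own first survey has no past alarm at all.

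A reader might also see contamination by the other condition. The extra gap before Visit 2 begins a week after Visit 1, and section 5 treats at least a week as enough for effects to dissipate. On the plan's own premise this is untreated time, so dilution is the right description.

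Finally, a reader might infer that Figure 1 contradicts the spacing rule for Visit 2, or that surveys were sent on stimulation days and coded to the wrong condition. The rule is a minimum of a week, and Day 9 to Day 17 is 8 days, which meets it. Nothing shows that any participant had the minimum interval or was surveyed on a visit day. What remains is a one-day difference for Visit 1: section 5 expects it 7 days after enrollment, whereas Day 1 to Day 9 is 8 days.

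It is also fair to say that deleting the survey does not recover an effect confined to the first day. It removes misattributed data and no more.

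**Conclusion.** The mismatch between recall window and coded condition is real and affects the outcomes of Hypotheses 1b and 2b. It is firm for the third EMA period: a mean window of about 8.6 days, about 88% of it before Visit 2. For the second period it is about 7.6 days or only a day or two, depending on when baseline EMA ran, so a week-long look-back should not be stated for both periods without that condition. The consequence is a dilution of about 4–5% of a constant active–sham effect, and more for a brief early one. These are averages; individual intervals are not given. They rest on participants taking the wording literally and on a first survey the day after the visit. This is a cheap improvement to the analysis and does not by itself threaten the conclusions.

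**What to change.** Assign each survey to condition by its timestamp relative to the stimulation session. Run the Q1, Q3 and Q4–Q7 models without the first survey of each EMA period, and without any survey whose look-back window includes a stimulation session. Keep Q14 and Q15 from those surveys, and state how the six-item composite is scored there, for example by setting it to missing.

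Data collection is complete, so the items can no longer be reworded. Label the exclusion post hoc and report it beside the analysis of all surveys.

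Reconcile section 7.1 with section 8 on when baseline EMA ran, and the 7-day expectation for Visit 1 in section 5 with Day 9 in Figure 1.

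The cost is a data-handling rule and about one survey in 21 per person per period for the look-back items, including one of the three on the first day after stimulation.
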